#### 9.4.3 ANALYSIS OF THE SECONDARY ENDPOINT(S)

N/A

---

#### 9.4.4 SAFETY ANALYSES

N/A

---

#### 9.4.5 BASELINE DESCRIPTIVE STATISTICS

Baseline descriptive statistics will be used to verify randomization procedures, including sex, campus, race/ethnicity, and suicide attempt history.

---

#### 9.4.6 PLANNED INTERIM ANALYSES

N/A

---

#### 9.4.7 SUB-GROUP ANALYSES

As part of the evaluation of feasibility/acceptability, we will examine whether features of the intervention were moderated by group-level factors such as age, sex, race/ethnicity, or history of formal mental health care.

---

#### 9.4.8 TABULATION OF INDIVIDUAL PARTICIPANT DATA

N/A

---

#### 9.4.9 EXPLORATORY ANALYSES

*All planned exploratory analyses should be specified in the protocol.*

Because pilot studies are not specifically powered for efficacy, we will examine if the pattern of change associated with receiving PF reports and/or supportive text messages are in the desired direction. We will also examine whether dose of an intervention (e.g., numbers of texts, number of weeks with texts,

number of personalized feedback reports) had a directional influence on mechanisms of interest. We will also explore whether randomization to the intervention group had an impact on mechanisms of interest relative to those in the assessment-only condition.

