With respect to randomization procedures, we will pre-randomize specific ID numbers and assign numbers sequentially based on completion of the baseline survey, blocking every 20 participants (15 Pilot MRT, 5 Assessment Only) to ensure balance. Those in the Pilot MRT condition will have further randomizations at the weekly level for six weeks, with each week randomized 2:1 to receive a Monday PF report, and each week randomized 2:1 to receive supportive text messages. As an MRT, we will not block for number of weeks receiving each intervention component, and participants may receive different 'doses' of the intervention components over the course of six weeks. Those randomized to receive supportive messages in a given week, as part of the Pilot MRT condition, will have a daily-level 50:50 randomization to receive or not receive a message. If randomized to receive a message on a given day, the message will be randomly pulled from a pool of 25 messages, with each message assigned a numerical value, and this message will be removed from the available pool once it has been received by a given participant. Participants will receive an average of 14 messages over the course of 6 weeks (i.e., ~4 weeks with messages x ~3.5 messages per week). This randomization will allow for the examination of within-person differences for weeks in which a participant is receiving PF reports versus not receiving PF reports, weeks receiving supportive messages versus not receiving supportive messages, between-person differences for volume of messages received at the weekly level, between-person differences for volume of messages or PF reports over the course of six weeks, and short-term (i.e., next-day) within-person changes associated with messages versus not receiving messages.

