Since this is a pilot study, our primary goals are to determine the feasibility and acceptability of the intervention components. We will utilize formal measures of feasibility and acceptability of the intervention components, including degree of agreement with specific statements regarding intervention features (e.g., frequency and timing of assessments, PF reports, and supportive messages; perceptions of confidentiality, helpfulness, usability, etc.), as well as objective data gathered from rates of attrition and adherence to study procedures (e.g., responding to surveys, clicking links to PF reports). While we are not designed to detect an intervention effect, we will explore whether patterns of change are in the desired directions for intervention components at the weekly level, and for overall between group differences in the Pilot MRT and Assessment only conditions. We will also utilize advanced statistical methods outlined in the training plan to identify predictors of change over the course of the study period, which will be used to inform the design of an adaptive version of this mobile intervention that will only send PF reports or messages under specific conditions.

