#### 4.2 SCIENTIFIC RATIONALE FOR STUDY DESIGN

An MRT allows individuals to serve as their own control and examine within-subject differences with respect to weeks receiving an intervention versus weeks not receiving an intervention. For this pilot study, we also opted to include a small assessment-only group as a control to examine trends in overall impact of having received the MRT intervention compared to not receiving any of the intervention components.

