#### 6.1.2 ADMINISTRATION AND/OR DOSING

Each participant ID will be pre-randomized to a specific sequence PF reports and text messaging, using a 2:1 ratio for weekly assignment to a PF report, and a 2:1 ratio for receiving text messages during a given week (with daily 50:50 randomization to message/no-message). Participants will, on average, receive 4 personalized feedback reports over the course of six weeks and will receive an average of 14 messages (average of 4 weeks receiving messages and 3.5 messages per week). As an MRT, there will be variation in dosage (e.g., some participants may receive 5 or 6 PF reports and some may receive 2 or 3) for the intervention components. This variability, whereby some weeks will include no texts/PF, PF and no texts, texts and no PF, or both PF and texts, will allow for comparisons that inform an eventual adaptive design.

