### 8 STUDY ASSESSMENTS AND PROCEDURES

## 8.1 ENDPOINT AND OTHER NON-SAFETY ASSESSMENTS

To recruit participants, we will obtain e-mail addresses of 2,500 first-year undergraduate students from the registrar (2,000 randomly selected from UM-Ann Arbor, and 500 from UM-Flint, which reflects the full annual enrollment of first-year undergraduate students at the UM-Flint campus) and invite them to participate in an 8-minute survey screen of their mental health, with an online consent form. We anticipate approximately 425 students will consent to participate and complete the **screening survey**, and that 142 students will meet criteria for a positive screen of mild-moderate depressive symptoms (PHQ-9 score of 5-14) and no current psychotherapy for the intervention portion of the study. We anticipate that 85% of the 142 participants who screened eligible for the study will continue to this next phase of the study, provide a cell-phone numbers, and complete the **baseline survey** (all within the same Qualtrics flow of the screening survey). The screening survey will be administered to all invited participants who consent to participate and takes approximately 8 minutes to complete. It will be sent out on a Tuesday, with reminders on Friday, and following Monday. Participants are deemed eligible if they score 5-14 on the PHQ-9, denoting mild-to-moderate depressive symptoms **and** report they are not currently enrolled in a form of mental health care (e.g., therapy). The baseline survey will be administered to participants screening positive on the screen, when they provide their cell phone number, and takes 10-15 additional minutes to complete. Randomization (3:1 to intervention versus assessment-only) occurs after baseline survey has been completed. Daily surveys will be administered to participants in the intervention group only, and take approximately 1 minute to complete, with links to the survey texted at 8pm each day. Weekly surveys are administered to all participants on Sunday evenings and take approximately ten minutes to complete. The final follow-up survey takes approximately 25 minutes to complete and will be administered to all randomized participants (n=120) on their sixth Sunday of the project. Administration of all surveys will be conducted via an online, automated system (Qualtrics).

[figure not shown]

Figure 1. Enrollment Flowchart

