#### 9.4 STATISTICAL ANALYSES

##### 9.4.1 GENERAL APPROACH

For descriptive statistics, categorical and continuous data will be presented via percentages, with ranges, means, and standard deviations when applicable. In keeping with an experimental therapeutics model, we will conduct exploratory analyses comparing the intervention and assessment-only group on the proposed mechanisms (e.g., coping self-efficacy, emotional awareness, readiness to seek-help). We will also be able to utilize multi-level models accounting for repeated assessments to examine associations of intervention components with mechanisms of interest at daily and weekly levels. With 50:50

randomizations for supportive text messages during ~4 week of the 6 weeks, there will be approximately 14 messages (3.5 per week x 4 weeks) for 90 participants, yielding approximately 1,260 next-day outcome datapoints. The six assessment points (five weekly assessments and final follow-up) will also allow for up to 540 outcomes (90 participants x 6 assessments) to compare associations of those randomized to receive PF reports and those who did not receive PF reports on a given week (360 with PF reports vs. 180 without PF). Model diagnostics will be utilized to determine whether corrections for autocorrelation or other model violations are necessary. We will utilize multiple imputation strategies to provide estimates and account for missing data, which is expected in the context of studies with daily assessments. Because pilot studies are not specifically powered for efficacy, we will examine if the pattern of change associated with receiving PF reports and/or supportive text messages are in the desired direction.

---

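### Exploratory PF-report, text and dose effects (and, in 4.1, the arm difference) are read by direction, with no promised interval and no baseline adjustment of the arm and dose comparisons

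*Combined protocol and SAP*

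**What the plan says.** The direction reading appears in three places.

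- **Components.** Section 9.4.9 says "we will examine if the pattern of change associated with receiving PF reports and/or supportive text messages are in the desired direction". Section 9.4.1 says the same.
- **Dose.** Section 9.4.9 asks whether the number of texts, of weeks with texts or of PF reports "had a directional influence on mechanisms of interest". Section 4.1 lists "between-person differences for volume of messages or PF reports over the course of six weeks" among the comparisons the randomization allows.
- **Arm.** Section 4.1 will explore whether "patterns of change are in the desired directions for intervention components at the weekly level, and for overall between group differences" between the two arms. Section 9.4.9 is looser and asks only whether assignment to the intervention arm had an impact on the mechanisms. Section 4.2 includes the small assessment-only arm "as a control to examine trends in overall impact of having received the MRT intervention".

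Section 9.4.1 plans multilevel models and multiple imputation. The summaries it names are percentages, ranges, means and standard deviations. Section 9.4.3, on the secondary endpoint, is marked not applicable.

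On baseline data, Section 8.1 says "Randomization (3:1 to intervention versus assessment-only) occurs after baseline survey has been completed". The Schedule of Activities (1.3) shows a full-scale score both before randomization and at 6 weeks for all six Section 3 outcomes (depression, anxiety, perceived stress, flourishing, coping self-efficacy, readiness to seek help). The same holds for emotional awareness, which 9.4.1 names as a mechanism for the arm comparison. In Section 9, the only role given to baseline measures that bears on these comparisons is verifying the randomization (9.4.5).

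**The concern.** A sign carries little information in a trial of this size. With no true effect, each estimate is favourable half the time. With a small true effect, the sign is often wrong. A sign also cannot show whether the data rule out a useful effect or an unhelpful one.

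This matters because the results have a stated use. Sections 2.1 and 6.1.2 say that the micro-randomizations and the comparisons they allow will inform an adaptive version of the intervention. Whoever designs that version needs the size of each effect and its uncertainty.

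The arm and dose comparisons are between people, and both are small. Adjusting them for the pre-randomization score of the same outcome would use data already in hand. Without it, precision is given up and chance baseline imbalance is left in the estimate.

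**Working it through.** **Inputs from the plan.** 120 participants, 90 in the micro-randomized arm and 30 assessment-only (4.1, 9.2). Six weeks, with PF reports and texts each randomized 2:1 by week and not blocked (4.1). Six weekly outcomes per person (9.4.1).

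**The plan's own counts reproduce.** 90 × 6 = 540 weekly outcomes; 540 × 2/3 = 360 with a PF report and 180 without; 90 × 14 = 1,260 message-days. The plan gives no interval width, effect size, SD, correlation or dropout rate, so those below are assumptions.

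**Arm contrast at 6 weeks (outcome SD units).**
- Unadjusted: SE = √(1/90 + 1/30) = 0.211; half-width 1.96 × 0.211 = 0.41.
- Baseline-adjusted: multiply by √(1 − r²), where r is the baseline to 6-week correlation.
- Change score: SE = 0.211 × √(2(1 − r)).

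| r | Adjusted SE | Adjusted half-width | Change-score SE |
|---|---|---|---|
| 0.3 | 0.201 | 0.39 | 0.249 |
| 0.5 | 0.183 | 0.36 | 0.211 |
| 0.7 | 0.151 | 0.30 | 0.163 |

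- Wrong sign, unadjusted, at a true 0.2 SD: Φ(−0.2/0.211) = 17%.
- At an assumed 80% follow-up (72 vs 24): SE 0.236; half-width 0.46 unadjusted and 0.44, 0.40 and 0.33 adjusted; wrong sign 20%.

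**PF dose slope (n = 90).** Assigned reports follow Binomial(6, 2/3).
- SD of dose = √(6 × 2/9) = 1.155; slope SE = 1/(√90 × 1.155) = 0.0913.
- Half-width 1.96 × 0.0913 = 0.179 SD per report.
- Section 6.1.2 expects that "some participants may receive 5 or 6 PF reports and some may receive 2 or 3". For 5 versus 3 reports the half-width is 2 × 0.179 = 0.36 SD; for 6 versus 2 it is 4 × 0.179 = 0.72 SD. The second is an extreme spread: 6 and 2 reports have probabilities of about 9% and 8%.
- Wrong sign: Φ(−0.05/0.0913) = 29% at a true 0.05 SD per report; Φ(−0.10/0.0913) = 14% at 0.10.

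**Weekly PF contrast (within-person SD units).**
- Information = 90 × (6 − 1) × (2/3)(1/3) = 100, so SE = 0.10 and half-width = 0.20.
- Wrong sign: Φ(−1) = 16% at a true 0.1; Φ(−2) = about 2% at 0.2.
- If 80% of weekly surveys are completed (assumed): 1.96/√(90 × 3.8 × 2/9) = 0.22.
- The weekly text contrast has the same 2:1 allocation and so the same width.

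The next-day text contrast is also planned (4.1, 9.4.1). I have not sized it.

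**Number of intervals.** Seven outcomes × six contrasts (weekly PF, weekly texts, arm, three dose measures) = 42, before any next-day contrasts. With no true effects, 42 × 0.05 = about 2 would exclude zero.

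**The case against.** The strongest reply is that this is a pilot without formal hypotheses (9.1), with a sample size not based on an effect (9.2), and that the direction wording is a deliberate limit on inference. Much of that stands. The absence of a test or of power is no fault here. The multilevel models and imputation will produce standard errors, so what is missing is a commitment to report them.

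Four stronger readings are tempting and should not be drawn:

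- **That components will be kept or dropped on sign alone.** No section says so. Section 4.1 says the adaptive design will be informed by predictors of change, found with methods in a training plan that is not among these documents.
- **That Section 9 reads the arm difference by direction.** It does not; only Section 4.1 does.
- **That omitting baseline adjustment biases the comparisons.** Arm and assigned dose are randomized, so the cost is precision and uncorrected chance imbalance.
- **That every sign is unreliable.** The weekly contrasts, the ones closest to the adaptive question, are fairly precise: at a true 0.2 within-person SD the sign is wrong only about 2% of the time.

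The gain from adjustment may also be small. At r = 0.3 the arm half-width moves only from 0.41 to 0.39 SD. Low correlations are plausible for the PHQ-9, because entry is restricted to scores of 5 to 14.

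The pilot label does not answer the core point. Low precision is what makes an interval more useful than a sign. Nor would reading the plan's references to change as change scores supply the adjustment: at r = 0.3 a change score is less precise than the unadjusted comparison, and at r = 0.5 it gains nothing.

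**Conclusion.** The concern holds as a reporting and precision gap in the exploratory analyses. PF, text and dose effects are read by direction, Section 4.1 adds the arm difference, no interval is promised, and available baseline scores are not used in the between-person comparisons.

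The between-person estimates are the weakest. The arm half-width is 0.41 SD, falling to between 0.39 and 0.30 SD with adjustment. The dose half-width is 0.18 SD per report. The weekly contrasts are tighter, at about 0.20 within-person SD.

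These widths assume complete data unless stated otherwise. The adjusted ones also assume correlations of 0.3 to 0.7, and the wrong-sign rates depend on the effect chosen. The primary feasibility and acceptability outcomes and the sample size are unaffected. The change is advisable; the trial's validity does not depend on it.

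**What to change.** Amend 9.4.1 and 9.4.9, and align 4.1:

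1. Replace the direction reading with each PF, text (weekly and next-day), assigned-dose and arm estimate reported with its 95% confidence interval. State that the intervals are exploratory and not adjusted for multiplicity, and that no conclusion is drawn from sign alone.
2. Adjust the 6-week arm comparison and the between-person dose models for the full-scale screening or baseline score of the same outcome. Use assigned dose, since 7.1 lets participants stop texts or reports and received dose may therefore differ from the randomized dose.

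Two clarifications are optional and not part of the defect: a study-week term in the weekly model, and common scoring of the abbreviated items at all six assessments for stress, coping self-efficacy and readiness, which are short-form weekly but full-scale at the sixth.

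The cost is wording only, because every covariate is already collected. The downside is that some results in the favourable direction will be shown as inconclusive, and a few of the many intervals may exclude zero by chance.

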#### 6.3 MEASURES TO MINIMIZE BIAS: RANDOMIZATION AND BLINDING

Participants will be assigned sequentially to Study ID numbers that have been pre-randomized with respect to study arm (3:1 ratio, blocking every 20 participants at 15:5). Each study ID will also have a randomized sequence for receiving or not receiving PF reports and/or text messages for weeks 1-6 of the study. Specific text messages will also be randomly pulled from a pool of messages, with previously

used message from a specific participant being pulled for subsequent randomizations (to not send the same message twice to same participant). Assessments are administered electronically and are all self-report. Thus, no blinding procedures are necessary.

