### 7 STUDY INTERVENTION/EXPERIMENTAL MANIPULATION DISCONTINUATION AND PARTICIPANT DISCONTINUATION/WITHDRAWAL

#### 7.1 DISCONTINUATION OF STUDY INTERVENTION/EXPERIMENTAL MANIPULATION

Participants have the option to withdraw from study participation at any time. Those in the intervention conditions will also have the option to withdraw from receiving texts or feedback reports while continuing participation in surveys and follow-up assessments.

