#### 9.3 POPULATIONS FOR ANALYSES

Analyses will be conducted using an intent-to-treat approach.

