#### 9.4.2 ANALYSIS OF THE PRIMARY ENDPOINT(S)

The primary outcomes include feasibility and acceptability measured by: (1) percentage of eligible participants who agree to participate, (2) percentage of completed follow-ups, (3) number of and reasons for withdrawals, (4) of those randomized to text-messages, percentage of participants who remain active (i.e. do not request to stop messages), (5) visits/clicks for an individual's personalized feedback report page, and (6) participant self-reported satisfaction with the intervention components.

---

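### Does the exploratory dose analysis in section 9.4.9 need to say whether dose means texts and reports assigned or received?

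*Combined protocol and SAP*

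**What the plan says.** All references are to the combined protocol and SAP.

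- **Section 9.4.9** states the analysis: "We will also examine whether dose of an intervention (e.g., numbers of texts, number of weeks with texts", followed by the number of feedback reports. The question is whether dose influenced the mechanisms in a particular direction.
- **Section 9.3** sets the rule for every analysis: "Analyses will be conducted using an intent-to-treat approach".
- **Section 6.1.2** explains why dose varies: "As an MRT, there will be variation in dosage".
- **Section 6.3** fixes the sequence before the trial starts: "Each study ID will also have a randomized sequence for receiving or not receiving PF reports and/or text messages for weeks 1-6" of the study.
- **Section 4.1** lists, among the contrasts that the randomisation makes possible, "between-person differences for volume of messages received at the weekly level".
- **Section 9.4.1** compares "those randomized to receive PF reports and those who did not receive PF reports on a given week", and gives the group sizes as 360 and 180.
- **Section 7.1** gives intervention participants the "option to withdraw from receiving texts or feedback reports while continuing participation in surveys and follow-up assessments".
- **Section 9.4.2**, item 4, makes the "percentage of participants who remain active (i.e. do not request to stop messages") a primary feasibility outcome.

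**The concern.** Nothing in 9.4.9 says assigned or received, and the wording elsewhere seems to pull both ways. Section 4.1 speaks of messages received, the sentence before the dose sentence in 9.4.9 speaks of receiving components, and 9.4.1 sets a randomised group against a group described by non-receipt.

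The two counts differ for anyone who opts out under 7.1 and still supplies outcomes. Assigned dose is random. Received dose is random except for the part lost to opt-out, which the participant chooses. If students who are doing badly stop the texts, low received dose goes with poor outcome and the slope tilts towards benefit. If students who have improved stop, it tilts the other way. Because 9.4.9 asks about direction and 9.1 sets no formal hypotheses, a tilt in the sign would bear on the main reading of this analysis, which is meant to help inform a later adaptive design.

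**Working it through.** **1. The plan's own figures, and what they count.** Inputs: weekly probability 2/3 for texts and for reports, daily probability 1/2, six weeks (6.1.2); 90 participants in the micro-randomised arm (9.2).

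- Text weeks: 6 × 2/3 = 4. Texts per text week: 7 × 1/2 = 3.5. Texts per person: 4 × 3.5 = 14. Total: 14 × 90 = 1,260.
- Weekly outcomes: 90 × 6 = 540. With a report: 540 × 2/3 = 360. Without: 540 × 1/3 = 180.

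All agree with 9.4.1, and all are expectations under assignment with no allowance for opt-out. So the comparison in 9.4.1 that seems to mix the two readings is counted by assignment; not receiving a report there is shorthand for being randomised to none.

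**2. The other passages side by side.**

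| Section | Wording | Reading |
|---|---|---|
| 9.3 | Intent-to-treat, no exception | Assigned |
| 6.1.2 | Variation attributed to the randomisation | Assigned |
| 6.3 | Sequence fixed per ID for weeks 1–6 | Assigned weekly dose exists for everyone |
| 9.4.1 | 360 and 180 | Assigned |
| 4.1 | Messages received, in a list of what the randomisation allows | Loose wording; context is assigned |
| 9.4.9 | Receiving, in the preceding sentence | Loose wording |

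The protocol uses receive and not receive throughout as names of the randomised conditions (for example in 1.1 and 4.1).

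**3. What the received reading would do.** The documents give no opt-out rate and no outcome difference, so these are assumptions: 90 participants, all with follow-up; outcome SD 1; opt-outs keep weeks 1 to k, with k uniform on 1–4; least-squares slope of outcome on number of texts; 6,000 simulated trials per setting. Variance of assigned texts = 6 × [2/3 × 7/4 + (2/3)(1/3) × 3.5²] = 6 × (1.167 + 2.722) = 23.3, so SD 4.83.

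Share of trials with a favourable slope when the true effect is zero:

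| Opt-out | Received, opt-outs 0.5 SD worse | Received, 0.5 SD better | Received, unrelated | Assigned |
|---|---|---|---|---|
| 2% | 56% | 43% | 50–51% | 49–52% |
| 5% | 63% | 37% | 50–51% | 49–52% |
| 10% | 74% | 26% | 50–51% | 49–52% |
| 20% | 86% | 14% | 50–51% | 49–52% |

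With a gap of 0.25 SD the shares are 53, 58, 62, 70% (worse) and 46, 43, 37, 29% (better).

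**4. The same selection against a real effect.** True effect 0.04 SD per text (0.04 × 4.83 = 0.19 SD per SD of dose), opt-outs 0.5 SD better, so that selection works against the effect:

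| Opt-out | Received | Assigned |
|---|---|---|
| 2% | 95% | 96% |
| 5% | 94% | 96% |
| 10% | 92% | 96% |
| 20% | 85% | 94% |

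For a very small effect, 0.01 SD per text, at 10% opt-out the shares are 45% received and 66% assigned.

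**5. A different selection model.** Let the odds of opting out depend on the underlying course, with an odds ratio of 1/3 to 3 per SD, and stopping after weeks 1–5. With a true effect of ±0.2 SD per SD of dose, the large-sample received slope keeps its sign up to 30% opt-out. With ±0.1 it keeps its sign at 5% opt-out; it can reverse at 10% with an odds ratio of 3 or 1/3, and at 20% with 2 or 1/2. The assigned slope keeps the true sign in every setting.

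**6. Price of the assigned reading.** Dilution factor = 1 − p(1 − 2.5/6), where 2.5 is the mean number of weeks kept: 0.971, 0.942 and 0.883 at p = 5, 10 and 20%.

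**The case for a change.** The strongest case for a change is that intent-to-treat is a single general sentence, placed under analysis populations. It does not define a dose variable or say how someone who stops after week 2 is counted, so an analyst who used messages received could point to 4.1 and claim to follow the protocol. The protocol expects opt-outs, since requests to stop messages are a primary feasibility outcome. Fixing the definition in advance would remove any temptation to choose the reading that gives the desired direction, and it would be cheap.

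Part of this stands. The definition is unwritten, the words in 4.1 and 9.4.9 are loose, and with no true effect the received slope is sensitive to selective opt-out. The calculations are not in dispute.

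The claim that the document truly points both ways does not stand. The phrase in 4.1 belongs to a sentence about what the randomisation permits, and the 9.4.1 comparison is counted at exactly two thirds and one third. An analyst who reads 9.3 with 6.1.2 and 6.3 arrives at assigned dose, and the weekly sequence needed to compute it already exists for every ID. Nor is the sign all that will be seen: 9.4.1 plans multilevel models, and nothing says that estimates will be withheld.

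**Conclusion.** No change follows. This is a missing detail that the rest of the plan fills: read with 9.3, 6.1.2, 6.3 and the counts in 9.4.1, dose in 9.4.9 is the randomised dose, and opt-out then only dilutes the slope, to about 94% of its true value at 10% opt-out.

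Harm would need three things together: an analyst departing from the intent-to-treat rule, opt-out related to outcome, and a true dose effect at or near zero. At 2% opt-out the shift is 6–7 points. Against 0.04 SD per text it is 4 points at 10% opt-out and 9 points at 20%. It is large only when the true effect is very small or nil, and with no true effect the assigned-dose sign is itself a coin toss at 49–52%, so a tighter definition would not make the direction informative there.

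The analysis is exploratory, in a pilot that 9.2 says is not sized to detect an effect, and the primary feasibility outcomes do not depend on it. All sizes rest on assumed opt-out rates, outcome gaps and complete follow-up; the documents supply none of these. The simulations cover text counts at length; the same reasoning applies to text weeks and feedback reports.
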